Lay Summary and Keywords Please provide the following information about your study. *Provide a brief lay summary describing this study. (limit 500 words). Pheochromocytoma is a catecholamine (ex. adrenaline) secreting tumor for which the primary treatment is surgical resection. Due to the hormones secreted by the tumor, alpha receptors on peripheral blood vessels are activated, causing constriction of these blood vessels and dangerously high blood pressure. During resection of the tumor, the source of excess hormone secretion is abruptly removed, which can lead to life-threatening blood pressure fluctuations during surgery. Alpha blockers are a class of medication that blocks the alpha receptor on blood vessels. Given preoperatively over a few weeks, these medications negate the effects of the excess hormones secreted by the pheochromocytoma, reducing the frequency and severity of dangerous blood pressure fluctuations intraoperatively and postoperatively. Preoperative alpha blockade is therefore critical to safely perform surgery to resect Phenoxybenzamine, a non-selective alpha blocker, is the most common medication used to alpha block patients prior to pheochromocytoma resection. However, due to increasing drug costs and increased side effects in comparison with selective alpha blockers, there is a renewed interest in studying alternatives to phenoxybenzamine. Selective alpha blockers such as doxazosin are also commonly used to alpha block patients prior to pheochromocytoma resection. Selective alpha blockers are significantly less expensive and are associated with fewer side effects than phenoxybenzamine. Most retrospective studies comparing phenoxybenzamine with selective alpha blockers show no difference in intraoperative blood pressure fluctuations, morbidity, or mortality in pheochromocytoma resection. The purpose of our study is to analyze preoperative, intraoperative, and postoperative outcomes in patients undergoing pheochromocytoma resection. We will compare a prospective group of patients who receive doxazosin (selective) for alpha blockade prior to surgery to a retrospective group of patients who received phenoxybenzamine (non-selective). Outcomes will include postoperative morbidity and mortality, intraoperative hemodynamic instability, quality of life, and cost. *List three to five keywords describing this study (separate the words with commas). The keywords may be used for identifying certain types of studies. pheochromocytoma, alpha blocker, randomized controlled trial * Is this study conducted or supported by HHS (e.g., the National Institutes of Health, Centers for Control and Prevention, etc.)? O Yes O No * Is this study regulated by the Food and Drug Administration (FDA)? O Yes No 4.1 If yes, check all that apply: **Human Drugs Medical Devices Biological Products**

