Given the difficulty in randomizing patients (high cost of phenoxybenzamine has caused a large portion of patients crossing over to the doxazosin arm, resulting in unbalance between the number of patients in each arm), patients who have been pre-treated with doxazosin before pheochromocytoma resection prospectively followed during the course of this study will be compared to a retrospective group of patients who were pre-treated with phenoxybenzamine.

Descriptive statistics including mean, median, standard difference, and frequencies will be calculated for each of the variables measured.

Differences in hemodynamic instability as indexed by specific vital sign parameters, ICU length of stay, inpatient length of stay, morbidity, mortality, cost, and quality of life will be analyzed with t tests or non-parametric tests as appropriate.

1.3 *If you will conduct genetic analysis with specimens, provide your assurance that the results will not be disclosed to subjects or used for clinical care.

Agree	
Not Applicable	

2.0 *Describe specimens and/or data that will be acquired without direct contact with study participants. Complete this item for each type used in the study:

usea in the stu	uy.	
Source	Data and/or Specimens Information	
View UCLA medical records	Data and/or Specimens? Indicate all that apply:	Data
	Indicate whether the data and/or specimens are pre-existing, at the time of this study, and/or if collection will be prospective:	Pre-existing
	Describe the data and/or specimens and indicate the original collection dates:	Electronic medical records from patients undergoing adrenalectomy for pheochromocytoma or paraganglioma from January 1, 2015 to present. Please see item 4.0 for further details on data to be collected from the EMR.
	Indicate the approximate number of data records and/or specimens to be collected:	50
	Will the specimens be used with animals?	No
	If yes, indicate the IACUC Number:	No Value Entered

*If any sources of data and/or specimens are not at UCLA, provide your agreement that the appropriate institutional approvals for release will be obtained (e.g., IRB approval).

Agree

•	
Not Applicable	
	o third parties, please contact the CTSI for directions about additional requirements. sources/pages/third_party
nttps://www.ctsi.ucla.edu/researcher-re	sources/pages/third_party
uttps://www.ctsi.ucla.edu/researcher-re	

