PATIENT ACQUISITION. All patients referred to the UCLA Department of Surgery requiring surgical resection of pheochromocytoma or paraganglioma will be counseled about surgery and the necessity for preoperative alpha blockade. The benefits and risks of the study will discussed, and the patient will be given the opportunity to enroll. Upon obtaining informed consent regarding enrollment in the study, the patient will be randomized to either receive preoperative blockade with either phenoxybenzamine or doxazosin.

PREOPERATIVE PREPARATION. The patient will then be referred to the UCLA Preoperative Evaluation and Planning Center (PEPC) for preoperative planning and optimization by an attending anesthesiologist. Additional testing such as echocardiography or stress testing will be pursed in accordance with preoperative risk-stratification in the standard fashion. A few weeks prior to surgery, the patient will initiate preoperative alpha blockade with the drug as determined by randomization. The drug will be titrated to a blood pressure of 120-130/80-85 in the standard fashion. Adjunctive beta blockers or calcium channel blockers may be initiated at the discretion of the physician.

Titration will be performed utilized the attached log ("Medication and Blood Pressure Log"), which will be emailed to the patient and will be returned by the patient by email every 2 days. The patients sitting and standing blood pressure will be used to titrate their alpha blocker dosage to prespecified targets as noted in the original IRB proposal. Heart rate will be logged to determine whether the patient requires adjunctive

specified targets as noted in the original IRB proposal. Heart rate will be logged to determine whether the patient requires adjunctive antihypertensive medications such as beta blockers or calcium channel blockers. This titration will take place over a period of 2-3 weeks. Once the patient's alpha blockade titration is complete, the log will be saved in a secure, encrypted server and will be linked with the patients record using non-identifying record ID.

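### The application still presents a randomised trial, but its stated comparison is non-randomised and by drug received, with no stated place for prospectively followed phenoxybenzamine patients

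*Combined protocol and SAP*

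**What the plan says.** Two descriptions of the study stand side by side in current text.

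**Randomised trial.** Under patient acquisition, section 10.1 item 4.0 states that "the patient will be randomized to either receive preoperative blockade with either phenoxybenzamine or doxazosin". The preoperative paragraph adds that the drug started is the one set by randomisation. Item 3.0 presents the study as, to the authors' knowledge, the first prospective randomised trial of the question. Risks & Benefits items 2.0 and 4.0 rest the value to society and the risk/benefit case on a randomised trial. The keywords in section 2.2 are "pheochromocytoma, alpha blocker, randomized controlled trial".

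**Non-randomised comparison.** The lay summary, also in section 2.2, says: "We will compare a prospective group of patients who receive doxazosin (selective) for alpha blockade prior to surgery to a retrospective group", that group having received phenoxybenzamine. Section 9.6 item 1.2 opens with "Given the difficulty in randomizing patients" and explains that the "high cost of phenoxybenzamine has caused a large portion of patients crossing over to the doxazosin arm, resulting in unbalance". Doxazosin-treated patients "prospectively followed during the course of this study will be compared to a retrospective group of patients who were pre-treated with phenoxybenzamine". The same item names the tests: hemodynamic and length-of-stay measures together with "morbidity, mortality, cost, and quality of life will be analyzed with t tests or non-parametric tests as appropriate".

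**Sources of data.** Section 9.6 item 2.0 takes about 50 pre-existing records of "patients undergoing adrenalectomy for pheochromocytoma or paraganglioma from January 1, 2015 to present". Section 20.1 item 1.1 keeps two groups apart: patients randomised to either drug, with signed consent, and the retrospective phenoxybenzamine cohort, for which a waiver is requested. Section 10.1 items 4.0 and 5.0 describe the SF-36 and adverse-effect data as five surveys, in person or by phone, from before blockade to one year after surgery.

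**The concern.** A reader of sections 10.1 and Risks & Benefits would expect a contrast protected by randomisation. The only between-group outcome tests in the visible text belong to a contrast without that protection. Patients are grouped by the drug they took, and the sponsor's own account is that cost moved many of them to doxazosin. Drug may therefore be confounded with patient mix, and possibly with treatment period. A finding of similar outcomes would be weaker evidence than the application says it will deliver.

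The second problem is grouping. Patients randomised to phenoxybenzamine are foreseen, since the consent section lists them separately from the retrospective cohort. Some of them may have taken the drug. The plan does not say whether they form their own group, join the retrospective group or are left out. This bears directly on quality of life, because surveyed patients who took phenoxybenzamine are the only evident source of survey responses on that drug.

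**Working it through.** The point turns on comparing sections, not on arithmetic.

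**The plan's own figure.** The one stated number that can be derived from others is the screening count: 62 / 0.85 = 72.94, rounded up to 73, which matches the text. It does not help here. The 62 is a maximum enrolment with no split by drug.

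**Step 1. Is the difference between current and superseded text?** No. The conflicting statements all stand in live items of the same application, and none is in an amendment log. Section 2.2 conflicts with itself, between lay summary and keywords.

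**Step 2. Does section 9.6 describe only a records sub-study?** Its item 1.0 is meant for research with no direct contact at all. Yet item 1.2 covers patients followed prospectively during the study, and the lay summary gives the same comparison for the study as a whole. The visible text of the statistics item in 10.1 lists descriptive statistics only. Item 1.2 is therefore the only visible place where between-group outcome tests are named, and those tests apply to the non-randomised groups.

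**Step 3. How are the groups formed?**

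- Doxazosin side: patients pre-treated with doxazosin and followed prospectively. By implication this includes patients assigned to phenoxybenzamine who crossed over.
- Phenoxybenzamine side: a retrospective group pre-treated with phenoxybenzamine.
- Prospectively followed and took phenoxybenzamine: on a plain reading, in neither group, unless the record window draws the patient in.

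The window starts on 1 January 2015 and has no closing date, so it may overlap enrolment. No visible text says whether it captures enrolled patients, and none prevents the same patient from being counted twice.

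**Step 4. Has randomisation stopped?** Section 10.1 item 4.0 uses the future tense and section 20.1 item 1.1 the past. No visible text says whether or when it stopped.

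**Step 5. What does this do to the quality-of-life test?** Item 1.2 tests quality of life between the groups. The data come from study surveys, two of them before surgery. The phenoxybenzamine side is pre-existing records under a consent waiver. Item 2.0 of section 9.6 refers to an item 4.0 for the data to be taken from the records. The natural reading is 10.1 item 4.0, which contains the survey paragraph. Nothing visible shows that historical records hold SF-36 responses. The comparator may therefore be small or absent.

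**Step 6. Can the size be put in numbers?** No. The documents give no crossover count, no number randomised and no number of phenoxybenzamine patients among the roughly 50 records, which are defined by operation and not by drug. Any confidence-interval width or share of patients would only restate assumed inputs.

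**The case against.** The strongest reply is that nothing is hidden. Section 9.6 item 1.2 names the change and its cause, the lay summary repeats the new comparison, and the consent section already separates the randomised patients from the retrospective cohort. That stands: a reader might infer that the sponsor is passing off a historical comparison as a randomised one, and the documents do not support that. The fault is that older sections were left unreconciled.

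Four further limits stand.

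- It is tempting to say that period is confounded with drug. The record window runs to the present and no accrual dates are given, so the groups may overlap in time. Period confounding is possible, not shown.
- It is tempting to say that there will be no SF-36 data at all on phenoxybenzamine. The pointer to item 4.0 leaves open that some such data come from the records, and prospectively followed patients may supply some.
- That any prospectively followed patient took phenoxybenzamine is an inference. The consent section shows assignment, not receipt, and a large portion crossing over only suggests that some did not.
- One might argue that such patients must be pooled with the retrospective group. The lay summary and item 1.2 define that side as retrospective, so pooling is one option among several.

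The attachments listed in 10.1, including the study variables and the timeline, were not supplied and could hold a grouping rule. They could not remove the conflict between the sections.

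**Conclusion.** The concern holds as a contradiction in current text together with a missing rule. The study claims randomised evidence, while its stated comparison is non-randomised and by drug received. That comparison cannot support the claim, whatever the true amount of crossover. On the visible text, prospectively followed phenoxybenzamine patients have no stated place in the analysis, and the quality-of-life test may have little or no comparator on that drug.

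Confidence in the contradiction is high, because it rests on the wording alone. The consequence for quality of life depends on two things that the documents do not settle: how many enrolled patients took phenoxybenzamine, and whether the records contain any survey data. No numerical size is claimed. The point should be corrected, since the correction is cheap and changes what the study can say it has shown.

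**What to change.** 1. **Reconcile the description.** Bring 10.1 items 3.0 and 4.0, Risks & Benefits items 2.0 and 4.0 and the keywords into line with the lay summary and 9.6 item 1.2. State whether and when randomisation stopped. Describe the main comparison as non-randomised and by drug received, and do not claim randomised evidence or a first randomised trial for it.
2. **State one grouping rule.** In 9.6 item 1.2 and in the statistics item of 10.1, say how prospectively followed phenoxybenzamine patients are handled: a separate group, inclusion with a flag, or stated exclusion. The choice is the sponsor's. Count each patient once where the record window overlaps enrolment. Tabulate all randomised patients by assigned and received drug.
3. **Limit the survey comparison.** Restrict the SF-36 and adverse-effect survey comparison to patients who completed the surveys, and give the number per drug. Report it descriptively if there are few or no phenoxybenzamine respondents.

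The work is protocol wording, one cross-table and a check for duplicate patients. The price is that the randomised-evidence claim is lost for the main comparison, and the survey comparison may rest on few phenoxybenzamine patients. The relabelling does not remove confounding; it makes the claim match the design.

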INTRAOPERATIVE PROTOCOL. Intraoperative hemodynamic monitoring will be conducted in the standard fashion, and a phenylephrine dose response curve will be generated by titration with phenylephrine to estimate the ED30 and therefore the effectiveness of the blockade. Surgery will proceed in the standard fashion. Times of induction, tumor manipulation, and adrenal vein ligation will be recorded. Vasopressors will be used at the discretion of the anesthesiologist.

POSTOPERATIVE PROTOCOL. Patients will be taken to the PACU for routine postoperative care. Admission to the surgical ICU will be performed at the discretion of the attending anesthesiologist and surgeon.

QUALITY OF LIFE / DRUG ADVERSE EFFECTS. Data regarding patient health related quality of life and drug adverse effects will be collected at five time points pre-blockade, post-blockade, and postoperatively at 3 months, 6 months, and 1 year. Health related quality of life data will be assessed utilizing the Short Form-36. Patients will be queried to specific adverse effects such as nasal congestion, headaches, palpitation, as well as their frequency and level of distress caused. Surveys will be complete in person during routine encounters or over the phone.

COST. Preoperative drug costs will be determined using the average wholesale price per unit multiplied by the number of units taken by the patient. Enrollment of the patient in Medicare and Medicare part D will be noted. Data regarding out of pocket drug costs will be collected. Inpatient costs will be calculated utilizing patient charges and the application of a charge to cost ratio.

4.1	* Will you be providing results of any experimental tests that
	are performed for the study?

o	Not Applicable
0	No
0	Yes - Complete Items 4.1.1 and 4.1.2

- 4.1.1 You indicated in Item 4.1 that the research involves experimental tests. Please describe the tests, provide a rationale for providing participants with the experimental test results and explain what, how and by whom participants and their health care provider will be told about the meaning, reliability, and applicability of the test results for health care decisions.
- 4.1.2 Will tests be performed by a Clinical Laboratory Improvement Amendments (CLIA) approved lab?

 Yes No

$^{5.0}$ *Indicate how much time will be required of the subjects, per visit or contact, and in total for the study.

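### The doxazosin v chart-phenoxybenzamine comparison may mix drug with intensity of titration monitoring, and the unadjusted plan cannot separate the two

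*Combined protocol and SAP*

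**What the plan says.** Section 9.6, item 1.2 of the combined protocol and SAP sets out the current design. Because cost drove many patients over to doxazosin, doxazosin patients "prospectively followed during the course of this study will be compared to a retrospective group of patients who were pre-treated with phenoxybenzamine". The same section gives the chart source as "Electronic medical records from patients undergoing adrenalectomy for pheochromocytoma or paraganglioma from January 1, 2015 to present", about 50 records. The groups are to be compared by t tests or non-parametric equivalents. No covariate, matching or restriction is mentioned. Item 1.1 gives the hypothesis that doxazosin is not inferior.

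Section 10.1, item 4.0 (Preoperative preparation) describes how enrolled patients are prepared. They use a medication and blood pressure log "which will be emailed to the patient and will be returned by the patient by email every 2 days". "This titration will take place over a period of 2-3 weeks". On the target: "The drug will be titrated to a blood pressure of 120-130/80-85 in the standard fashion". On other drugs: "Adjunctive beta blockers or calcium channel blockers may be initiated at the discretion of the physician". The completed log is stored under the patient's study record ID, and section 10.1, item 1.0 lists it among the study materials.

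Item 4.0 still assigns both drugs by randomisation. Section 20.1, item 1.1 mentions signed consent from patients randomised to either drug, separately from the retrospective phenoxybenzamine cohort.

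**The concern.** The titration procedure was written for two randomised arms that would both receive it. Under section 9.6 the comparator now comes from charts, and the visible text does not extend the log to those patients. It also sets no entry condition for them beyond having been pre-treated with phenoxybenzamine. So the groups may differ in how closely treatment was supervised as well as in drug.

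This matters because section 10.1, item 3.0 says that preoperative blockade reduces the frequency and severity of pressure fluctuations. Quality of preparation is thus taken to influence intraoperative haemodynamic instability, a listed outcome. If closer titration helps, doxazosin gains an advantage that does not come from the drug, in the direction of the study's own hypothesis. Adjusting for patient characteristics would not remove it, because the difference lies in how treatment was delivered.

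**Working it through.** **The plan's own figure.** The only sample-size figure that can be derived is the screening number under Characteristics of the Study Population: 62 / 0.85 = 72.9, rounded up to 73. It reproduces, and this point does not depend on it. The 62 itself has no stated inputs. No margin, SD or alpha is given for the main comparison.

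**The sections side by side.**
- Monitoring: log every 2 days for enrolled patients; not stated for chart patients.
- Duration: 2-3 weeks for enrolled patients; no minimum stated for chart patients.
- Pressure target: one band, described as standard practice; no difference between groups is shown.
- Adjunct drugs: at the physician's discretion for enrolled patients; not stated for chart patients.
- Data to be abstracted: section 9.6 refers to item 4.0, whose visible text names no duration of blockade, dose changes or achieved pressure to be taken from charts.
- Analysis: unadjusted.

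The documented asymmetry is therefore the log and its schedule.

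**Monitoring contacts.** 14 / 2 = 7 and 21 / 2 = 10.5, so about 7 to 10 review points per enrolled patient. The number for chart patients is unknown.

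**Illustration with a binary outcome (all inputs assumed).** Suppose instability is 20% in well-titrated and 40% in under-titrated patients on either drug, and 90% of doxazosin patients are well titrated.
- Chart patients 60% well titrated: doxazosin 0.9 × 0.20 + 0.1 × 0.40 = 22%; phenoxybenzamine 0.6 × 0.20 + 0.4 × 0.40 = 28%. That is a 6-point advantage with no drug effect.
- In general the artefact is 0.20 × (0.9 − p), where p is the proportion of chart patients well titrated. It is 6 points at p = 0.6 and 0 at p = 0.9. At p = 1.0 it is 0.20 × (−0.1), or 2 points against doxazosin.

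**Illustration with a continuous outcome (bias and group sizes assumed).** Let the log alone improve the outcome by b SD in the doxazosin group, with doxazosin truly worse by exactly the margin. At one-sided 0.025 the chance of falsely declaring non-inferiority is Φ(b/se − 1.96), with se = √(1/n₁ + 1/n₂). This does not depend on the margin chosen.
- 62 v 50: se = 0.190. For b = 0.2, Φ(1.05 − 1.96) = 18%. For b = 0, 0.1, 0.3 and 0.5 the results are 2.5%, 7.6%, 35% and 75%.
- 31 v 31: se = 0.254. For b = 0.2, Φ(0.79 − 1.96) = 12%. For b = 0, 0.1, 0.3 and 0.5 the results are 2.5%, 5.9%, 22% and 50%.

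A negative b, meaning better-monitored chart patients, would lower the error rate below 2.5%.

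**The case against.** The strongest reply is that the plan's silence about chart patients does not show a difference. Several parts of this reply stand.

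- A reader might infer that only enrolled patients were titrated to a fixed target. The text presents that target as standard practice, so no difference in target is shown.
- A reader might infer that chart patients had merely routine dosing. Their titration is undocumented, which is a weaker statement. Section 10.1, item 5.0 counts only questionnaires as extra study time, and section 9.2a describes direct-contact activities as usual practice, so the log may have been close to normal care. Against that, it is filed as a study material and linked to a study record.
- A reader might infer that only doxazosin patients used the log. Section 20.1 refers to patients randomised to phenoxybenzamine, section 9.6 says that many rather than all crossed over, and the record window runs to the present. Some phenoxybenzamine patients may have used it.
- The titration protocol and the study variables list are attachments that are not shown. The fields wanted here may already be in them, and the cost analysis already needs the number of drug units taken.
- A reader might think the comparison fails because ED30, obtained by "titration with phenylephrine to estimate the ED30 and therefore the effectiveness of the blockade", is a prospective measurement. ED30 is neither a listed outcome nor a tested variable, so its absence in chart patients breaks no planned comparison.
- Using sitting and standing readings alongside one summary band is not a clear contradiction, since the detailed targets are held in a proposal that is not shown.

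What remains is that nothing visible makes monitoring comparable between the groups, and the stated analysis has no means of telling its effect from that of the drug.

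**Conclusion.** The point holds as a risk of confounding that the visible plan neither measures nor addresses: drug may be mixed with monitoring intensity, and unadjusted tests cannot separate them. If closer titration helps and chart patients were monitored less closely, the bias favours a non-inferiority finding for doxazosin. Both conditions are assumptions.

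The size is unknown. The illustrations show only that a modest titration effect could matter at sample sizes of this order. They use assumed rates and biases, and group sizes that the plan does not fix for this comparison.

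It would go too far to say that the study can support no claim about the drug. The drug-price part of cost is less affected: the Risks & Benefits section quotes maximum unit prices of $197.79 and $1.42, a gap that titration intensity does not create. This is a cheap improvement.

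**What to change.** In section 9.6, item 1.2:

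1. Abstract from the record for both groups, with the same definitions and time window: dates of first and last alpha-blocker dose, number of dose changes, final daily dose, adjunct drugs, surgery date, and the last recorded blood pressure after blockade and before induction. That pressure should come from neither the home log nor a preoperative evaluation (PEPC) reading that predates blockade. Report all of these by group. If the study variables list already contains them, say so.
2. Add a sensitivity comparison that applies one documented-course criterion, such as duration of blockade, to both groups. Restricting only the chart group would select one arm. Treat achieved pressure as descriptive, because the drug itself affects it.
3. Report separately any phenoxybenzamine patients treated under the study procedure. They are the only ones who could show the log's effect apart from the drug's.
4. State that the contrast is study-monitored doxazosin v phenoxybenzamine as recorded in charts, and limit the conclusion to the preparation strategy unless titration is shown to be similar.
5. Reconcile section 10.1, item 4.0 (both drugs, randomised) with section 9.6 (chart comparator).

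The cost is some extra chart abstraction, a smaller restricted comparison and a more modest headline claim. No dose or target is proposed.
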